### **3.6. Procedure for Unblinding/Unmasking due to a Life-Threatening Adverse Event, Early Termination of a Participant, or Determination of Whether a Participant Stopping Rule Has Been Met**

If a CoFAR Grade 4 systemic allergic reaction or other life-threatening adverse event (AE) occurs and knowledge of the treatment assignment is required, the study treatment may be unblinded. Unblinding must be approved by the Division of Allergy, Immunology, and Transplantation (DAIT)/ NIAID Medical Monitor unless the DAIT/NIAID Medical Monitor is not accessible. In the event of an emergency, the investigator or designated qualified individual may obtain the participant's blinded treatment assignment via the validated system. Upon performance of a blind break, the system will send out a blinded notification to alert Statistical and Clinical Coordinating Center and NIAID staff. In the case of an accidental or emergency unblinding outside of the system, the site investigator will notify the DAIT/NIAID Medical Monitor and the SACC team of the unblinding event by the next business day, following the unblinding. The unblinding will also be reported to the NIAID Asthma and Allergy Data and Safety Monitoring Board (DSMB).

In the event of early termination of a participant ([Section 12.2](#)), the request for non-emergent participant unblinding must be assessed and approved by the DAIT Medical Monitor. Unblinding approval may not be granted until data entry for the participant is complete. Once unblinded, a participant cannot re-enroll in the study and will be responsible for obtaining any subsequent doses of COVID-19 vaccine, if applicable. Refer to the MOP for additional details.

In the event a participant has had a reaction to the first injection or becomes pregnant following the first injection, it will be necessary to unblind the participant to determine whether the participant received placebo or vaccine and whether the participant has met a stopping rule or requires counseling prior to continuing in the study. The site should inform Rho and the DAIT Medical Monitor of the need for unblinding. The participant's assignment should be unblinded after the review of the diary on day 4, so that the participant may be informed if ineligible to continue, or counseled as to their options by an investigator if they remain eligible, and queried as to their wish to receive further injections.

A full account of each unblinding event will be recorded, including the date and time of the unblinding, the reason for the decision to unblind, and the name of the individual who made the decision, and the names of the Medical Monitor and others who were notified. The reasons for unblinding of a participant's treatment will be included in the final study report.

Unblinding the study due to an approved interim analysis, final analysis, or study termination will require written approval from the DAIT/NIAID Medical Monitor.

All IND expedited safety reports will be reported to the FDA, IRBs, and DSMB in an unblinded fashion.

## **4. Selection of Participants**

### **4.1. Rationale for Study Population**

The occurrence of allergic reactions after administration of the new mRNA lipid nanoparticle vaccines has caused anxiety in the public, especially among those who have experienced severe allergic reactions to foods, insect stings, or medications. In the pediatric age group, most individuals with severe asthma are highly allergic as evidenced by multiple sensitivities to aeroallergens. Currently, there are questions about the urgency for vaccination among those with severe allergic asthma as the data on risk is unclear. Pediatric onset asthma has been found to confer a decreased risk of COVID-19; however, poorly controlled pediatric asthma has been correlated to an increased risk of hospitalization. In addition to the highly allergic, there are individuals who have mast cell disorders which predispose them to life-threatening reactions to otherwise innocuous triggers. The mechanism of the vaccine reactions

is not known; the majority of people experiencing these reactions have had a history of “allergies” and a substantial number have reported a history of anaphylaxis, but careful evaluations of these individuals have not been conducted. Therefore, this study is designed to determine whether people with a recent history of severe allergic reactions to foods, allergen immunotherapy, insect stings, or allergic reactions to drugs or vaccines, or those with poorly controlled allergic asthma or mast cell disorders (HA/MCD group) are at increased risk for an allergic reaction compared to a comparison group without severe allergic disease or mast cell disorders. While it is possible that this HA/MCD group is not truly at the highest risk for allergic reactions to these SARS-CoV-2 vaccines, allergic and mast cell diseases that have the potential to produce serious allergic reactions are highly prevalent, and a study that reassures individuals with such conditions will positively impact the acceptability of the vaccine. Moreover, this will likely encompass individuals with milder allergic diseases who may also have second thoughts getting vaccinated.

In the event we do see a significant number of reactions, it would be important to be able to reliably ascertain relatedness to vaccination (hence exclusion of any allergen immunotherapy within the 24 hours prior to or after the vaccination, or other vaccination within 14 days). Similarly, we hope to begin to understand the mechanisms of reactions so have excluded medication use that would be expected to interfere with analysis in mechanistic studies. This includes medications such as immunomodulators including systemic steroids, biologics including type 2 inhibitors, as well as others such as rituximab, and the 5 LO inhibitor Zileuton. To minimize risks, we are excluding participants with underlying conditions or other medications that, in the opinion of the investigator, may increase risk in the event of an anaphylactic reaction or lead to complications following administration of epinephrine, including but not limited to, those with coronary artery disease, peripheral or cerebral vascular disease, unstable angina, cardiac arrhythmia other than supraventricular tachycardia (SVT), medically unstable hypertension, unstable asthma or symptomatic asthma on the day of vaccination, or with current use of beta-blockers, angiotensin-converting-enzyme (ACE) inhibitors, monoamine oxidase (MAO) inhibitors, tricyclic anti-depressants or other agents that could interfere with the treatment of anaphylaxis in the opinion of the investigator ([Section 4.3](#)). Finally, we do not anticipate many of the recruited individuals will meet current criteria for high risk for COVID-19, which are the only pregnant individuals the ACIP and CDC suggest should consider vaccination after a discussion with their physician, thus we are excluding pregnant women from enrolling, though they may elect to receive the second vaccination if they become pregnant during the 3 - 4 weeks between vaccinations.

As the pandemic has continued, the emergency use approvals have been expanded to younger ages over time. To date, the enrollment in DAIT-COVID-19-004 has been very largely adults. To ascertain if age is a risk factor for reaction, beginning under protocol version 5.0, children aged 5 to 17 years will be enrolled. The Pfizer-BioNTech COVID-19 Vaccine is currently approved for individuals 5 to 15 years of age under EUA and 16 years or older under full licensure. A phase 2/3 study is currently underway for the Moderna COVID-19 Vaccine in children from age 6 months to age 11 years ([Section 1.3](#)). Both because school aged children have not been assessed for the incidence of systemic allergic reactions to the mRNA vaccines and because they have a higher rate of food allergy-induced anaphylaxis than adults, it is important to include them in the assessment of reactions.

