### 3. Study Design

#### 3.1. Description of Study Design

This is a multi-center, randomized, initially blinded, phase 2 trial to assess SARS-CoV-2 vaccination reactions in two populations: one population including individuals with a history of recent, severe allergic reactions, poorly controlled allergic asthma, or MCDs and one comparison population without severe allergies or mast cell disorders. The study aims at enrolling up to 2040 HA/MCD and 1360 comparison participants across approximately 30 US sites.

Approximately two-thirds of participants enrolled in each of the 2 groups will be female. This is because the vast majority of cases of anaphylaxis to the COVID-19 vaccines have occurred in women. Enrollment of participants who qualify only on the basis of reactions to multiple unrelated drugs will be limited to approximately 300. Enrollment of the MCD group is anticipated to be at least 200 participants, and not more than 300 participants.

Participants enrolled under protocol versions 1.0 – 4.0 were randomized 2:2:1:1 to receive the Pfizer-BioNTech COVID-19 Vaccine, Moderna COVID-19 Vaccine, placebo + Pfizer-BioNTech COVID-19 Vaccine, or placebo + Moderna COVID-19 Vaccine (Figure 1).

Participants enrolled under protocol versions 5.0 – 8.0 will be randomized 2:1 to receive the Pfizer-BioNTech COVID-19 Vaccine or placebo + Pfizer-BioNTech COVID-19 Vaccine. If enrollment is robust and sustained, active vaccine randomization may be changed to Moderna.

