### 3.5. Stratification, Randomization, and Blinding/Masking

#### 3.5.1. Stratification and Randomization

Randomization will be performed using a validated system configured by the Statistical and Clinical Coordinating Center (SACCC) that automates the random assignment of vaccine groups to study ID numbers. The randomization scheme will be generated by one statistician and reviewed and approved by another statistician at the SACCC.

Under protocol versions 1.0 – 4.0, participants were randomized 2:2:1:1 to receive either the Pfizer-BioNTech COVID-19 Vaccine, Moderna COVID-19 Vaccine, placebo + Pfizer-BioNTech COVID-19 Vaccine, or placebo + Moderna COVID-19 Vaccine. Participants randomized to one of the placebo groups received placebo as a first dose and received two doses of their assigned active vaccine at subsequent visits.

Under protocol versions 5.0 – 8.0, participants will be initially randomized 2:1 to receive the Pfizer-BioNTech COVID-19 Vaccine or placebo + Pfizer-BioNTech COVID Vaccine. If enrollment is robust and sustained, the active vaccine may be changed to Moderna, and participants will then be randomized 2:1 to receive Moderna COVID-19 Vaccine or placebo + Moderna COVID-19 Vaccine.

Randomization will be stratified by site, sex, population (HA/MCD or comparison), and mast cell disorder/idiopathic anaphylaxis (yes or no) within the HA/MCD group. Randomization will occur in permuted blocks with varying block sizes randomly distributed. Randomization data will be kept strictly confidential, accessible only to authorized persons, until the time of unblinding. The clinical site's research pharmacy will dispense the study drug as per the randomly assigned treatments.

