# R: Primary Analysis (Barnard's) p-value
library(exact2x2)
t <- with(d_1 %>% filter(dose == 'E' and protocol<5),
table(group,resp))
uncondExact2x2(t[1,2],sum(t[1,]),
t[2,2],sum(t[2,]),
alternative = "less",
parmtype = "difference",
method   = "score",
midp     = TRUE,
control  = ucControl(nPgrid=5000),
conf.int = FALSE)
```

Exact unconditional confidence limits for the risk difference are obtained with SAS procedure PROC FREQ and the RISKDIFF option in the EXACT statement. These RISKDIFF options request exact unconditional 95% confidence limits for the risk (proportion) and risk difference for the 2x2 table respectively. PROC FREQ computes the confidence limits by the tail method, which inverts two separate one-sided exact tests of the risk difference, where the tests are based on the score statistic (Chan and Zhang 1999). The size of each one-sided exact test is at most $\alpha/2$, and the confidence coefficient is at least $(1-\alpha/2)$.

If there is an issue with the calculation of the Barnard's Exact Unconditional Test, we will perform the Risk difference estimates, asymptotic 95% confidence intervals, and p-values using SAS procedure PROC FREQ and the RISKDIFF option without an EXACT statement.

```
*** Primary Analysis (Asymptotic);
proc freq data = d_1 order = data;
  title "Primary";
  where dose = 'E' and protocol<5;
  tables group*resp / riskdiff;
run;
```

Additionally, we will compare the proportion of participants experiencing a systemic allergic reaction (as defined in section 7.2.1) between HA/MCD adult (18 years and older at enrollment) and HA/MCD child (less than 18 years of age at enrollment) populations for each vaccine separately. Children who qualified for the study on the basis of uncontrolled allergic asthma will be excluded from this analysis. The point estimate of the difference in proportions between adult and child populations within each vaccine will be estimated along with its corresponding 95% exact unconditional confidence interval. The proportion difference will be tested using a Barnard's Exact Unconditional Test with a two-sided test using the central method of doubling the one-sided p-value. No multiplicity adjustment will be applied.

In the event that there are not enough subjects in a particular population, the reaction rate will be described descriptively.

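### The adult–child comparison in HA/MCD is not adjusted for entry route and drops asthma entrants among children only, so its estimate of an age effect may be biased by case mix

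*Protocol*

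**What the plan says.** Protocol 4.1 states why children were added: "To ascertain if age is a risk factor for reaction, beginning under protocol version 5.0, children aged 5 to 17 years will be enrolled". It gives as one reason that "they have a higher rate of food allergy-induced anaphylaxis than adults", and notes that enrolment up to that point had been overwhelmingly adult.

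SAP 7.2.2 sets the comparison "between HA/MCD adult (18 years and older at enrollment) and HA/MCD child (less than 18 years of age at enrollment) populations", for each vaccine separately. It reports the "difference in proportions between adult and child populations within each vaccine" with an exact unconditional interval, and the difference is to be "tested using a Barnard's Exact Unconditional Test with a two-sided test using the central method of doubling the one-sided p-value". Protocol 14.4.3 plans the same difference and interval without naming a test. Neither text stratifies, standardises or adjusts for how a participant qualified.

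There is one restriction: "Children who qualified for the study on the basis of uncontrolled allergic asthma will be excluded from this analysis". Asthma is criterion 7 in protocol 4.2. It carries no age limit, and the list applies to all cohorts unless stated otherwise, so adults who entered by asthma stay in.

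HA/MCD status needs any one of eight criteria. Protocol 3.1 says "Enrollment of the MCD group is anticipated to be at least 200 participants, and not more than 300 participants" and limits entrants qualifying only by reactions to several drugs to about 300. Neither figure is split by age. Protocol 3.5.1 stratifies randomization by, among others, "mast cell disorder/idiopathic anaphylaxis (yes or no) within the HA/MCD group".

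Three other provisions touch on entry route. Protocol 14.4.4 has exploratory covariate and risk-factor analyses, protocol 14.4.5 allows optional descriptive breakdowns by inclusion criterion, and SAP 5.2 presents details of cohort assignment. None is tied to the age comparison.

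**The concern.** Age is not randomized. The mast cell/idiopathic anaphylaxis stratum balances treatment arms, not adults against children. A crude adult–child difference therefore mixes any effect of age with any difference in the kind of allergy that brought people in.

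Bias needs two things together: a route mix that differs by age, and a reaction risk that differs by route. On the first, the documents offer only the higher rate of food-induced anaphylaxis in children and the largely adult early cohort. On the second, protocol 4.1 says mast cell disorders predispose to life-threatening reactions, but no document gives a risk by route.

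The asthma exclusion shows that the plan accepts that entry route can distort this contrast. As written it is one-sided, which can add an imbalance rather than remove one.

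At stake is the estimate and interval reported for a named secondary objective. There is also a knock-on effect: protocol 14.4.4 pools adults and children if their proportions look similar, and case mix could make them look similar or different.

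**Working it through.** **Plan's own figures.** No power or sample size is stated for adult v child. The nearest figures reproduce. For children, 180 v 120 at 0.05 v 0.0001 gives 79.6% power with a two-sided unconditional exact test (protocol 14.7: approximately 80%). For 2/180 the exact 95% interval is 0.0013 to 0.0396 (protocol: 0.001 to 0.039).

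**Sizes used.** 1020 adults and 180 children in HA/MCD per vaccine (protocol 14.7). The 180 is before the asthma exclusion. It also assumes that children from versions 5.0–8.0 enter this comparison; SAP 7.2.1 limits the primary analyses to versions 1.0–4.0 and 7.2.2 does not say which rule applies here.

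**Assumed mixes.** If the protocol 3.1 limits applied to adults in proportion, mast cell entrants would be 200/2040 = 9.8% to 300/2040 = 14.7%, and drug-only entrants 300/2040 = 14.7%. Adults are therefore taken as 10–15% mast cell and 15% drug-only, and children as 0–3% and 0–5%. These shares by age are assumptions.

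**Formula.** Crude rate in an age group = Σ (route share × route risk), with the same route risks in adults and children. The true age effect is zero, so any difference is case mix.

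| Assumed risk: mast cell / drug / other | Adults | Children | Adult − child (points) |
|---|---|---|---|
| 4% / 2% / 0.5%, widest | 0.15×4 + 0.15×2 + 0.70×0.5 = 1.25% | 0.50% | +0.75 |
| same, narrowest | 0.10×4 + 0.15×2 + 0.75×0.5 = 1.075% | 0.03×4 + 0.05×2 + 0.92×0.5 = 0.68% | +0.40 |
| 5% / 0.5% / 0.5% | 0.95–1.175% | 0.50–0.635% | +0.32 to +0.68 |
| 2% / 1% / 1% | 1.10–1.15% | 1.00–1.03% | +0.07 to +0.15 |
| 0.5% / 0.5% / 2%, widest | 0.30×0.5 + 0.70×2 = 1.55% | 2.00% | −0.45 |
| same, narrowest | 0.25×0.5 + 0.75×2 = 1.625% | 0.08×0.5 + 0.92×2 = 1.88% | −0.26 |

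**Against sampling error.** SE = √[pA(1−pA)/1020 + pC(1−pC)/180]. For 1.25% v 0.5% it is 0.63 points, for 1.075% v 0.68% it is 0.69, and for 1.55% v 2.0% it is 1.11. The widest positive shift is about one standard error.

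**Against the test.** The check enumerates all outcomes and doubles the one-sided Barnard p-value, with the common rate searched over its whole range. The crude test rejects 0.04% of the time at 1.25% v 0.5%, 0.3% at 1.075% v 0.68%, and 4.1% at 1.55% v 2.0%. With 1% in both ages it rejects 1.6%. Limiting the search to common rates up to 6% gives 1.5%, 0.6% and 4.6% for the three shifted cases. None passes 5%.

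**More extreme inputs.** Suppose adults are 20–29% mast cell or drug (29% = 600/2040, both limits filled by adults alone) and children 0–5%. Risks of 5% v 1% then shift the difference by 0.60 to 1.16 points, with rejection at most 0.4%. At 10% v 1% the shift is 1.35 to 2.61 points, with rejection of 2% to 19%. The highest rejection at these shares is 27%, at 10% v 0.5%.

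**What the mast cell stratum alone removes.** Take the first row outside the mast cell stratum. Adults are at (0.15×2 + 0.70×0.5)/0.85 = 0.76% and children at 0.50%, so 0.26 of the 0.75 points remain. In the widest reversed case, (0.15×0.5 + 0.70×2)/0.85 = 1.74% against 2.00% leaves −0.26 of −0.45. Stratifying helps but does not finish the job, which is why the food-restricted comparison belongs beside it.

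**The case against.** The strongest reply is that the size rests wholly on assumption. The criteria are the same at every age, the mast cell and drug limits are not split by age, and protocol 3.5.1 gives no reason for its stratum. A reader might infer that adults entered by mast cell and drug routes and children by food. The documents do not say that; the food remark in protocol 4.1 is a reason to include children, not a description of who enrolled. All of this stands.

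Next, sampling error dominates. At a child risk of 0.5–0.68%, 180 children yield 180×0.005 = 0.9 to 180×0.0068 = 1.2 expected events, and the chance of none is 0.995^180 = 41% to 0.9932^180 = 29%. A reader might infer that the trial will declare a false age effect. The rejection rates above do not support that for the assumed mixes, and SAP 7.2.2 falls back to description if a population is too small. This also stands, and it rules out a finely stratified analysis as the main estimate.

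The asthma rationale in protocol 4.1 is paediatric, so few adults may have entered that way. The documents do not say; if so, a symmetric exclusion costs almost nothing.

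What does not stand is the suggestion that the existing provisions cover the point. The covariate work is exploratory, the breakdown by inclusion criterion is optional, and neither changes the adult–child estimate.

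**Conclusion.** The concern holds as a possible bias in the estimate. The comparison is meant to show whether age is a risk factor, it is crude over eight pooled entry routes, and its one case-mix control is applied to children only. Under the assumed mixes and risks with no age effect, the shift is about −0.45 to +0.75 percentage points (ratio 0.78 to 2.5). That is comparable to the 1% planning rate, though seldom enough alone to make the test significant. It is close to nil where risks differ little by route, and larger only if some routes carry risks near 10%. The direction cannot be known from the documents. Neither the claim that case mix will be reported as an age effect, nor a stated adult excess of mast cell and drug routes, is supported.

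**What to change.** In SAP 7.2.2 and protocol 14.4.3:

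1. Apply the asthma exclusion to both age groups, and state how someone who also meets another criterion is handled.
2. Tabulate qualifying criterion by age group.
3. Keep the crude exact difference but label it descriptive and unadjusted. Pre-specify beside it (a) a risk difference stratified by mast cell disorder/idiopathic anaphylaxis, with weights and interval method named in advance, and (b) an exact comparison in both ages restricted to participants whose qualifying trigger was food. Criteria 1 and 2 also cover venom, immunotherapy and latex, so (b) must use the trigger, not the criterion number.
4. Do not attribute a crude difference to age unless these analyses agree, and say beforehand what agreement means (for example, same direction and similar size).

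The cost is SAP and protocol wording and one or two tables. The randomization factor is already recorded, and the existing asthma exclusion already needs the qualifying criterion; the food trigger is assumed to be recorded with it. The downside is wider intervals, and with about one child event expected at the lower assumed risks the added analyses may be inconclusive. In that case the report should say that age and allergy type could not be separated.

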#### 4.2. Inclusion Criteria

Note criteria apply to all cohorts and protocol versions, unless otherwise stated.

Individuals who meet all of the following criteria are eligible for enrollment as study participants:

Both groups:

1. Participant and/or parent/legal guardian must be able to understand and provide informed consent and/or assent, as applicable

2. Male or non-pregnant female 12 years of age or older on the date of first study vaccination/placebo administration (protocol versions 1.0 – 4.0) **OR** male or non-pregnant female 5 -17 years of age on the date of first study vaccination/placebo administration (protocol versions 5.0 – 8.0)
3. Females of childbearing potential must have a negative pregnancy test prior to the first vaccination and placebo administration, if applicable. If a participant becomes pregnant after receiving a placebo dose but prior to receiving study vaccination, she will be discontinued from the study.
4. Females of reproductive potential\* and sexually active must agree to use FDA approved methods of birth control for the duration of the study. These include hormonal contraceptives, intrauterine device, double barrier contraception (i.e., condom plus diaphragm), or male partner with documented vasectomy.  
\*Menopause is defined as at least 12 consecutive months without menses; if in question, a follicle stimulating hormone of  $\geq 25$  U/mL must be documented. Hysterectomy, bilateral oophorectomy, or bilateral tubal ligation must be documented, as applicable; if documented, women with these conditions are not required to use additional contraception.

